#### **2) Information on the safety of Humira**

- ① List of adverse drug reactions (ADRs)/infections
- ② Factors which may affect the safety of Humira
  - Incidence of ADRs by patient background factor
  - Incidence of ADRs before and after increase in Humira dose
- ③ Adverse events occurring during or after the treatment period
  - List of occurrences of serious adverse events
- ④ Errors in administration during self-injection

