## 2. Definition of terms and abbreviations

The terms and abbreviations used in this statistical analysis plan are defined as follows.

Terms and abbreviations	Definition
Adverse events	An adverse event refers to any unfavorable and unintended sign (including an abnormal laboratory finding), symptom or disease associated with the use of a drug, whether or not considered related to the drug.
Adverse events during the safety analysis period	Adverse events that occurred during the period up to the start date of Humira treatment + 196 days.
Adverse events outside the safety analysis period	Adverse events that occurred prior to the start date of Humira treatment or after the start date of Humira treatment + 196 days.
Adverse reactions	Of adverse events, events for which causal relationship with Humira cannot be ruled out are defined as adverse reactions.
Adverse reactions during the safety analysis period	Of adverse events during safety analysis period, events for which a causal relationship with Humira cannot be ruled out are defined as adverse reactions during safety analysis period.
Adverse reactions outside the safety analysis period	Of adverse events outside safety analysis period, events for which a causal relationship with Humira cannot be ruled out are defined as adverse reactions outside the safety analysis period.
Basic statistics	Basic statistics include sample size, mean value, standard deviation, minimum value, median value, maximum value, first quartile and third quartile.
MedDRA/J	Medical Dictionary for Regulatory Activities/Japanese edition
SOC	MedDRA/J System Organ Class
PT	MedDRA/J Preferred Term
CDAI	Clinical Disease Activity Index
CRP	C-Reactive Protein
DAS	Disease Activity Score
DMARDs	Disease Modifying Antirheumatic Drugs
EULAR	European League Against Rheumatism
ESR	Erythrocyte Sedimentation Rate
JIA	Juvenile idiopathic arthritis
MTX	Methotrexate
NSAIDs	Non-Steroidal Anti-Inflammatory Drugs
SDAI	Simplified Disease Activity Index
VAS	Visual Analog Scale

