Administration by a doctor	In “2. Status of Humira treatment” in the registration form, administration is “administration by a doctor” at all timings.
Dosage and administration category: Dose increase group (20 mg → 40 mg)	In “2. Status of Humira treatment” in the registration form, “dose” was increased from 20 mg to 40 mg.
Dosage and administration category: Maintained dose group	In “2. Status of Humira treatment” in the registration form, “dose” was never increased or reduced.
Dosage and administration category: Other	In “2. Status of Humira treatment” in the registration form, “dose” was reduced to below 20 mg, “dose” was increased from 40 mg to 80 mg, “dose” was increased and then reduced, or “number of doses” is other than biweekly.
Patients deviated from	Patients who received Humira at a dose other than “20 mg/2 weeks”

Name of data	Derivation and calculation methods
recommended dosage and administration of Humira	or “40 mg/2 weeks” are defined as patients deviated from the recommended dosage and administration.
Previous medications	Of the drugs listed under “Status of administration of concomitant drugs” in “5. Previous medications for juvenile idiopathic arthritis” in the CRF and confirmed to have been administered between the start date of Humira treatment - 90 days and the start date of Humira treatment - 1 day, drugs falling under “MTX”, “DMARDs”, “steroid (oral + injection)” or “NSAIDs (oral + injection)” in “Drug code list_20171012.xlsx” are defined as previous medications.
Status of previous medications	“With previous medications” should be selected when the patient was previously treated with medications, “unknown/unspecified” should be selected when “Status of previous medications for juvenile idiopathic arthritis” is not specified or indeterminable, and “without previous medications” should be selected otherwise.
Previous medication: Methotrexate	“With previous medication: methotrexate” should be selected when the conditions for “previous medications” are met and the previous medication falls under “MTX” in “Drug code list_20171012.xlsx”, “unknown/unspecified” should be selected when the status of previous medications is “unknown/unspecified”, and “without previous medication: methotrexate” should be selected otherwise.

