Data	Layer separation
disorder	
Complication: Cardiovascular disorder	No, yes, unknown/unspecified
Complication: Blood disorder	No, yes, unknown/unspecified
Complication: Respiratory disorder	No, yes, unknown/unspecified
Complication: Other	No, yes, unknown/unspecified
History of allergy	No, yes, unknown/unspecified
Breakdown of history of allergy	Drug, food, other
Previous medications	No, yes, unknown/unspecified
Breakdown of previous medications	Methotrexate, corticosteroid, NSAIDs, other DMARDs
History of treatment with previous medications (biological products)	No, yes, unknown/unspecified
Breakdown of history of treatment with previous medications (biological products)	Tocilizumab, etanercept, other
Concomitant drugs	No, yes, unknown/unspecified
Breakdown of combination drugs	Methotrexate, corticosteroid, NSAIDs, other DMARDs, other drugs
Tuberculin skin test	Tested, not tested, unknown/unspecified
Quantiferon test (including T-SPOT)	Tested, not tested, unknown/unspecified
Chest x-ray	Tested, not tested, unknown/unspecified
Chest CT	Tested, not tested, unknown/unspecified
Immunology test (tuberculin skin test or Quantiferon test or T-SPOT)	No, yes, unknown/unspecified
Image testing (chest x-ray or chest CT)	No, yes, unknown/unspecified
Prophylactic administration (status of prophylactic administration by	No, yes, unknown/unspecified

Data	Layer separation
implementation status of tuberculosis tests)	
HBs antigen test	Implemented (negative, positive, unknown/unspecified, subtotal), not implemented, unknown/unspecified
HBs antibody test	Implemented (negative, positive, unknown/unspecified, subtotal), not implemented, unknown/unspecified
HBc antibody test	Implemented (negative, positive, unknown/unspecified, subtotal), not implemented, unknown/unspecified
Status of Humira treatment (dosage and administration)	20 mg/2 weeks, 40 mg/2 weeks, 20 mg/2 weeks → 40 mg/2 weeks, other
Number of doses	≥1 to <2 doses, ≥2 to <6 doses, ≥6 to <12 doses, ≥12 doses
Days to the date of the last dosing	1 to 28 days, 29 to 84 days, 85 to 168 days, ongoing at day 169
Dose at the start of Humira treatment	20 mg, 40 mg, 80 mg, other, unknown/undescribed
Dosage and administration category	Dose increase group (20 mg → 40 mg), maintained dose group, other, unknown/unspecified
Self-administration	No, yes, unknown/unspecified
Error caused by self-administration	No, yes, unknown/unspecified

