Purpose of analysis: The number and percentage of patients will be calculated for each implementation status (tested, not tested, unknown/unspecified) of hepatitis B test (HBs antigen test, HBs antibody test, HBc antibody test). Where tests were performed, the number and percentage of patients will also be calculated for breakdown of their results (negative, positive, unknown/unspecified).

Note: None in particular.

“Table 1.8 Status of Humira treatment (dosage and administration)”

Analysis object: Patients included in the safety analysis set

Purpose of analysis: For the status of Humira treatment (dosage and administration) (20 mg/2 weeks, 40 mg/2 weeks, 20 mg/2 weeks → 40 mg/2 weeks, other), the number and percentage of patients will be calculated.

Note: Patients who received doses other than “20 mg/2 weeks”, “40 mg/2 weeks”, “20 mg/2 weeks

→ 40 mg/2 weeks” should be categorized into “other”.

“Table 1.9 Status of Humira treatment (number of doses, days to the date of the last dosing)”

Analysis object: Patients included in the safety analysis set

Purpose of analysis: For the status of Humira treatment (number of doses, days to the date of the last dosing), the number and percentage of patients will be calculated by category defined in “11. Data-layer separation”.

Note: Where the last record of the treatment status is checked for “ongoing” or where the end date of treatment exceeds the start date of treatment + 168 days, the end date of treatment should be handled as the start date of treatment + 168 days.

“Table 1.10 Dose by body weight at the start of treatment”

Analysis object: Patients included in the safety analysis set

Purpose of analysis: The number and percentage of patients will be calculated for each category of dose at the start of Humira treatment as defined in “11. Data-layer separation” (number of doses, days to the date of the last dosing) by body weight at the start of Humira treatment (<15 kg, ≥15 kg and <30 kg, ≥30 kg, unknown/unspecified).

Note: The denominator of the percentage of the number of patients should be patients included in the safety analysis set.

“Table 1.11 Incidence rate of administration errors caused by self-injection”

Analysis object: Patients included in the safety analysis set

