#### “Table 2.9 Incidence of adverse reactions in patients who received an increased dose”

Analysis object: Patients included in the safety analysis set

Purpose of analysis: Adverse reactions during the safety analysis period will be aggregated in accordance with “11. Data-layer separation” (dosage and administration category) as shown below. The number of patients analyzed, the number and percentage of patients who experienced adverse reactions, the number of adverse reactions, the number of patients who experienced adverse reactions

by type of adverse reaction (by SOC and PT) and their percentages against the patients analyzed will be calculated.

Number of patients who experienced adverse reactions: Number of patients who experienced adverse reactions.

Number of adverse reactions: Number of adverse reactions that occurred. When a single patient experienced multiple episodes of the same adverse reaction (PT), they should be counted as one event.

Types of adverse reactions: Should be calculated by SOC and by PT. Output data should be sorted in the order of international agreements and in the ascending PT code order. When a single patient experienced multiple episodes of the same adverse reaction (PT), they should be counted as one event.

Note: The version of MedDRA/J used should be provided.

“Table 2.10 Incidence of adverse reactions in patients who self-administered Humira”

Analysis object: Patients included in the safety analysis set

Purpose of analysis: Adverse reactions during the safety analysis period will be aggregated in accordance with “11. Data-layer separation” (self-administration) as shown below. The number of patients analyzed, the number and percentage of patients who experienced adverse reactions, the number of adverse reactions, the number of patients who experienced adverse reactions by type of adverse reaction (by SOC and PT) and their percentages against the patients analyzed will be calculated.

Number of patients who experienced adverse reactions: Number of patients who experienced adverse reactions.

Number of adverse reactions: Number of adverse reactions that occurred. When a single patient experienced multiple episodes of the same adverse reaction (PT), they should be counted as one event.

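### No SAP table gives the before-versus-after-dose-increase ADR incidence that the protocol lists; Table 2.9 pools the two periods under a whole-course dose category

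*SAP*

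**What the plan says.** **Protocol, section 9(1) 2), safety of Humira.** One listed item is "Incidence of ADRs before and after increase in Humira dose". It is not restricted to any particular step in dose.

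**SAP 13.2, Table 2.9.** Adverse reactions in the safety analysis set are "aggregated in accordance with “11. Data-layer separation” (dosage and administration category) as shown below". Section 11 gives that variable four layers: increase (20 mg → 40 mg), maintained, other, and unknown/unspecified. Repeat episodes of one PT in one patient count once.

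**SAP section 2.** The period counted is defined by "Adverse events that occurred during the period up to the start date of Humira treatment + 196 days".

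**SAP 10.1** defines the categories:
- Increase: "dose” was increased from 20 mg to 40 mg".
- Maintained: "dose” was never increased or reduced".
- Other: "dose” was reduced to below 20 mg, “dose” was increased from 40 mg to 80 mg, “dose” was increased and then reduced", or a frequency that is not biweekly. There is no residual clause.

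**SAP 13.1, Table 1.8**, on a different variable, does have a catch-all: doses outside its named patterns, the last ending in "40 mg/2 weeks” should be categorized into “other".

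**The concern.** The protocol item is a contrast in time around an event, the increase. Table 2.9 is a contrast between patients classified by what happened over their whole course. The second does not answer the first:

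- A reaction before the increase is attributed to the increase group.
- A PT that appears before and recurs after the increase is one event, so recurrence is hidden.
- A patient has to stay on treatment long enough to be increased. One who stops early after a reaction at an unchanged dose falls in the maintained group. Increase versus maintained therefore mixes dose with time on treatment.
- The increase group holds only 20→40 mg, so an increase from 40 to 80 mg goes to Other.

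Followed exactly, the SAP leaves a safety question listed in the protocol without a result. A reader of Table 2.9 could take reactions that preceded the increase as reactions of patients on the higher dose.

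**Working it through.** The plan gives no figure on this point. Its one design figure, 95% probability of seeing a 3% ADR in 100 patients, reproduces (1 − 0.97^100 = 0.952), but nothing here depends on it.

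**Step 1. Does any SAP output split at the increase?**

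| Output | Split used | Before/after the increase? |
|---|---|---|
| Table 2.9 | Whole-course dose category | No |
| Tables 2.14, 2.15 | Four-week blocks from treatment start | No; increases need not fall at a common week |
| Tables 2.16.1, 2.16.2 | During versus after treatment | No |
| Table 4.2 | Listing: event onset date, initial and maximum dose | No date of increase |
| Table 4.3.2 | Listing: dated dose rows | No adverse reactions |

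Tables 4.2 and 4.3.2 both carry the case number, so the split could be built by hand, but no incidence is specified. SAP 10.2 merges same-PT events when the dataset is created, so a hand split may miss repeat onsets.

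**Step 2. How much could be pooled?** The documents give neither the number of patients with an increase nor its timing. For illustration only, assume follow-up to day 196, an increase at day d, and a reaction rate after the increase that is RR times the rate before. The share of reactions that precede the increase is d / (d + RR × (196 − d)).

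- RR = 1: 28/196 = 14%, 84/196 = 43%, 140/196 = 71% for an increase at week 4, 12 or 20.
- Week 12, RR = 2: 84/(84 + 224) = 27%. Week 12, RR = 0.5: 84/(84 + 56) = 60%.
- Extremes of the nine combinations: 28/(28 + 336) = 8% and 140/(140 + 28) = 83%.

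This shows only that the share depends on timing. It is not an estimate.

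**Step 3. How precise would the missing result be?** With assumed counts, 3 of 10 patients has an exact 95% interval of 7–65%, and 9 of 30 has 15–49%.

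**Step 4. Are the dose categories complete?** Apply the SAP 10.1 definitions literally to biweekly courses.

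- Doses 20 and 40 mg, one change: 20→40 is Increase; 40→20 fits nothing, because it is a reduction but not to below 20 mg.
- Section 11 foresees start doses "20 mg, 40 mg, 80 mg, other, unknown/undescribed". Adding 80 mg gives six single changes. Four fit nothing: 40→20, 20→80, 80→20 and 80→40.
- Overlap: 20→40→20 and 20→40→80 meet both Increase and Other. A constant dose not given biweekly meets both Maintained and Other.

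**The case against.** The strongest reply is that nothing is lost: onset dates and dated dose records are both planned outputs, and the result would be descriptive and very imprecise. The first half stands as far as it goes. This is a gap in specification, and a reader who inferred that the data are not collected would be wrong. But data in two listings are not an incidence, and imprecision is a reason to label the result, not to omit it. The protocol lists an incidence, not a powered test.

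Four stronger readings are tempting and are not supported:

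- *A given share of reactions is misattributed.* Every input in step 2 is assumed.
- *Patients drop out of Table 2.9.* SAP 9.10 requires breakdown percentages to total 100% and double-counted items to be footnoted. It arguably does not reach a table of incidence within strata, but silent omission would sit badly with it, and a programmer may well treat Other as residual. What can be said is that placement is unspecified.
- *Four of six patterns unassigned means most dose changes are affected.* That is a count of hypothetical courses. Three of the four involve 80 mg, which SAP 10.1 already classes as a deviation from the recommended dosage. The 40→20 mg case alone makes the point.
- *Dose is taken from the wrong form.* SAP 10.1 cites the registration form, while the protocol lists dosage under the CRF. The forms are not available here, and this looks like a labelling slip with no stated effect on any result.

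**Conclusion.** The point holds. The protocol lists ADR incidence on either side of a dose increase, and the SAP nowhere produces it. Table 2.9 counts earlier reactions in the increase group and collapses recurrences of the same PT. This should be corrected, because it concerns a listed safety result and not only a missing detail. The conclusion rests on the wording of the two documents and on no numerical assumption. The size of the effect cannot be known from them.

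The category wording is secondary: Other is a closed list, some known courses have no stated place, and some have two. The number of patients affected is likewise unknown.

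**What to change.** **Main change: a descriptive panel in Table 2.9.**

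1. Define in SAP section 10 the group of patients with any recorded dose increase, whatever their dose category, and use it also for the increased-dose flag in Table 4.3, which has no derivation of its own.
2. Count patients and events by SOC and PT with onset before versus on or after the date of first increase. Give the number of patients and the patient-time in each period.
3. Apply the one-per-PT rule within each period, using records from before the same-PT merge where needed.
4. Show separately the reactions that cannot be placed because the onset date or the increase date is unknown; SAP 9.2 sets incomplete dates to unknown.
5. For a course such as 20→40→20 mg, either end the after period at the later reduction or show and footnote the time beyond it.
6. Label the contrast descriptive, imprecise and confounded by time since start.

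**Secondary change.** Make Other residual in SAP 10.1, as Table 1.8 does for its own variable, and state which category takes precedence when a course meets two. This must not remove anyone from the panel above.

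**Cost.** SAP wording, one added panel and no new data collection. The adverse event dataset may have to be re-derived, since SAP 10.2 merges same-PT events when the dataset is built.

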#### “Table 2.14 Frequency of serious adverse reactions”

Analysis object: Patients included in the safety analysis set

Purpose of analysis: Of adverse reactions during the safety analysis period, serious adverse reactions will be aggregated in accordance with “11. Data-layer separation” (timing of onset of adverse events) as shown below. The number of patients analyzed, the number and percentage of patients who experienced serious adverse reactions, the number of serious adverse reactions, the number of patients who experienced serious adverse reactions by type of serious adverse reaction (by SOC and PT) and their percentages against the patients analyzed will be calculated.

Number of patients analyzed: Number of patients receiving treatment by period.

Number of patients who experienced serious adverse reactions: Number of patients who experienced serious adverse reactions during the administration period. When a single patient experienced multiple episodes of the same serious adverse reaction (PT), the event that occurred at the earliest time should be counted as one case.

Number of serious adverse reactions: Number of serious adverse reactions that occurred during the administration period. When a single patient experienced multiple episodes of the same serious adverse reaction (PT), the event that occurred at the earliest time should be counted as one case.

Types of serious adverse reactions: Should be calculated by SOC and by PT. Output data should be sorted in the order of international agreements and in the ascending PT code order. When a single patient experienced multiple episodes of the same serious adverse reaction (PT), the event that occurred at the earliest time should be counted as one case.

Note: The version of MedDRA/J used should be provided.

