- 6) Investigators will fill out the case report form for each patient following the 24-week observation period without delay, and provide it to a medical representative. When a patient discontinues treatment during the observation period, the investigator will follow up the patient until the end of the 24-week observation period, fill out the case report form for him/her at the end of the observation period, and provide it to a medical representative.
- 7) The sponsor will confirm the contents of the registration and case report forms, and perform reinvestigation whenever necessary.
- 8) Medical representatives will also visit investigators once every week or every other week, in principle, to monitor for the occurrence of adverse events, provide proper use information, and determine the progress of patient registration.
- 9) Following the 24-week observation period, the investigator will evaluate each patient for malignancy annually for 2 years after the initiation of Humira treatment using a separate follow-up investigation form. When the occurrence of malignancy is found in a patient, the investigator will perform detailed investigation of him/her. Investigators will be instructed to report the occurrence of malignancy to the sponsor without delay when they are found, regardless of the timing of follow-up investigation.
- 10) Adverse Event Reporting  
In the event of a serious adverse event, and additionally, any non-serious events of malignancy in patients 30 years of age and younger, whether related to adalimumab or not, if applicable - the physician will notify the AbbVie contact person (Medical Representative in Japan) within 24 hours of the physician becoming aware of the event.

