Priority survey item	Infection, tuberculosis, interstitial pneumonia, malignant tumour, congestive cardiac failure, autoimmune disease, pancytopenia, demyelinating disease, administration site reaction
Status of previous medication: biological products	No, yes, unknown/unspecified
Status of previous medication: MTX	No, yes, unknown/unspecified
Status of previous medication: corticosteroid	No, yes, unknown/unspecified
Status of previous medication: NSAIDs	No, yes, unknown/unspecified
Status of previous medication: Other DMARDs	No, yes, unknown/unspecified
Status of concomitant drug: MTX	No, yes, unknown/unspecified
Status of MTX: details	<4 mg/m  /week, ≥4 mg/m  /week and <7 mg/m  /week, ≥7 mg/m  /week

Data	Layer separation
	and <10 mg/m  /week, ≥10 mg/m  /week, dose per body surface area unknown
Status of concomitant drug: corticosteroid	No, yes, unknown/unspecified
Status of concomitant drug: NSAIDs	No, yes, unknown/unspecified
Status of concomitant drug: Other DMARDs	No, yes, unknown/unspecified
Combination therapy for juvenile idiopathic arthritis	No, yes, unknown/unspecified
Combination therapy for juvenile idiopathic arthritis: details	Rehabilitation, other, unknown/undescribed
Duration of combination use of MTX for juvenile idiopathic arthritis	No, yes, unknown/unspecified
Duration of combination use of MTX for juvenile idiopathic arthritis: details	After the start of Humira treatment up to the end date of Humira treatment, at least a dose used during Humira treatment, unknown/unspecified
Timing of onset of adverse events	From the start of treatment and within 4 weeks of treatment, after Week 4 of treatment and within 8 weeks of treatment, after Week 8 of treatment and within 12 weeks of treatment, after Week 12 of treatment and within 16 weeks of treatment, after Week 16 of treatment and within 20 weeks of treatment, after Week 20 of treatment and within 24 weeks of treatment, after Week 24 of treatment

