#### “Table 2.15 Frequency of adverse reactions”

Analysis object: Patients included in the safety analysis set

Purpose of analysis: Adverse reactions during the safety analysis period will be aggregated in accordance with “11. Data-layer separation” (timing of onset of adverse events) as shown below. The number of patients analyzed, the number and

percentage of patients who experienced adverse reactions, the number of adverse reactions, the number of patients who experienced adverse reactions by type of adverse reaction (by SOC and PT) and their percentages against the patients analyzed will be calculated.

Number of patients analyzed: Number of patients receiving treatment by period.

Number of patients who experienced adverse reactions: Number of patients who experienced adverse reactions during the administration period. When a single patient experienced multiple episodes of the same adverse reaction (PT), the event that occurred at the earliest time should be counted as one case.

Number of adverse reactions: Number of adverse reactions that occurred during the administration period. When the same adverse reaction (PT) occurs multiple times in the same case, the event that occurred at the earliest time is counted as one case.

Types of adverse reactions: Should be calculated by SOC and by PT. Output data should be sorted in the order of international agreements and in the ascending PT code order. When the same adverse reaction (PT) occurs multiple times in the same case, the event that occurred at the earliest time is counted as one case.

Note: The version of MedDRA/J used should be provided.

“Table 2.16.1 List of adverse events that occurred during and after treatment”

Analysis object: Patients included in the safety analysis set

Purpose of analysis: Adverse events during the safety analysis period will be aggregated for the entire population, patients ongoingly treated at Week 24 of treatment, and discontinued patients (during treatment, after treatment, overall) as shown below.

During treatment: Adverse events that occurred after the start date of Humira treatment by the end date or the date of discontinuation of Humira treatment

After treatment: Adverse events that occurred after the end date or the date of discontinuation of Humira treatment by the start date of Humira treatment + 196 days

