Case number, administration method category (at the start of treatment, during treatment), consultation category at the start of treatment, dose (dose at the start of treatment, maximum dose, dosing intervals), number of daily doses (maximum), change in treatment status, administration period (start date of treatment, end date of treatment), discontinuation of treatment (yes/no, reason for discontinuation, drug name after switching), flag identifiers (patients included in the safety analysis set, patients included in the efficacy analysis set, patients deviated from recommended dosage and administration of Humira, patients who received an increased dose).

Note: For flag identifiers, “○” (applicable) or “-” (not applicable) should be output.

“Table 4.3.2 List of patients in whom a dose of Humira was changed”

Analysis object: Patients with fixed CRFs

Purpose of analysis: A list of summary of patients analyzed will be created for the following items:  
Case number, administration method category, consultation category, body weight, dose, administration period (start date of treatment, end date of treatment), reason for the change in dose, discontinuation of treatment (yes/no, reason for discontinuation).

Note: Multiple rows per patient should be output so that dose increase/reduction can be seen.

“Table 4.3.3 List of status of treatment with previous medications”

Analysis object: Patients with fixed CRFs

Purpose of analysis: A list of summary of patients analyzed will be created for the following items:  
Case number, drug category, drug name, route of administration, administration period (start date of treatment, end date of treatment), status of Humira treatment (start date of treatment, end date of treatment), flag identifier (patients included in the safety analysis set, patients included in the efficacy analysis set).

Notes: • Patients with previous medications should be output.  
• For flag identifiers, “○” (applicable) or “-” (not applicable) should be output.

“Table 4.3.4 List of concomitant drugs and concomitant therapies”

Analysis object: Patients with fixed CRFs

Purpose of analysis: A list of summary of patients analyzed will be created for the following items:  

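### Tables 2.14 and 2.15 do not pair numerator and denominator: the SOC/PT rows and the after-Week-24 class fail however the undefined administration period is read

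*SAP*

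**What the plan says.** **Denominator.** Tables 2.14 (serious adverse reactions) and 2.15 (all adverse reactions), SAP section 13.2, both use "Number of patients analyzed: Number of patients receiving treatment by period". The count falls as patients discontinue.

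**Event pool.** Table 2.14 begins "Of adverse reactions during the safety analysis period, serious adverse reactions will be aggregated in accordance with" the onset classes of SAP section 11, and Table 2.15 does the same for all reactions. SAP section 2 sets the safety analysis period by calendar time alone: "Adverse events that occurred during the period up to the start date of Humira treatment + 196 days". Treatment status plays no part.

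**Onset classes.** SAP section 10.2 counts days from the start date as Day 1. Six four-week classes run to Day 168, and a seventh covers Day 169 onward. Section 10.2 labels the seventh as after the end of treatment. Section 11 requires it in the tables: "after Week 20 of treatment and within 24 weeks of treatment, after Week 24 of treatment".

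**Numerator rows.** The patient-count row of Table 2.14 reads "Number of patients who experienced serious adverse reactions during the administration period", and that of Table 2.15 reads "Number of patients who experienced adverse reactions during the administration period". The event-count rows carry the same limit. The rows by SOC and PT do not, yet their percentages are also taken against the patients analysed.

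**Meaning of the limit.** Neither section 2 nor section 10 of the SAP defines administration period. The patient listings (Table 4.3 and those after it) use the term for a pair of dates: "administration period (start date of treatment, end date of treatment".

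**Follow-up and end date.** When a patient stops treatment early, protocol section 6(3) says "the investigator will follow up the patient until the end of the 24-week observation period". SAP section 10.1 caps the end date of treatment at start + 168 days for patients who are ongoing or treated longer.

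**The concern.** A percentage by interval is interpretable only if everyone who can enter the numerator is in the denominator. Here the denominator depends on treatment status, while the pool and the classes do not. Discontinued patients stay under follow-up, so their later reactions are in the pool after they have left the denominator. Whether those reactions are counted turns on an undefined term that is applied to some rows and not to others. Two programmers could follow the text faithfully and produce different percentages.

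At stake is the time pattern of reactions. Incidence and conditions of occurrence are a stated purpose of the surveillance (protocol section 1). Among the planned tables, only these two show reaction percentages by time since start.

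**Working it through.** The plan states no by-period figure, discontinuation rate or reaction rate to reproduce. The target of 100 patients (protocol section 2) serves only as a round N below. The discontinuation counts and risks are assumptions.

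**Step 1. Day mapping.** With the start date as Day 1, start + 168 days is Day 169 and start + 196 days is Day 197. The last class therefore has 197 − 169 + 1 = 29 days.

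**Step 2. Overall rows, Days 1–168.**
- *Reading A: administration period means treatment start to end.* Reactions after discontinuation are left out. Numerator and denominator are both on-treatment, and the inflation factor is 1.00.
- *Reading B: it means the onset interval.* Let N be all patients, m those discontinued before the class, r the on-treatment risk in the class, and k the ratio of off-treatment to on-treatment risk. The percentage is r × [(N − m) + k × m] / (N − m). The inflation factor is 1 + k × m / (N − m), which equals N / (N − m) when k = 1.

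Reading B with N = 100 and r = 10%:

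| Discontinued (m) | Factor, k = 0.5 | Factor, k = 1.0 | Percentage shown | On-treatment percentage |
|---|---|---|---|---|
| 5 | 1.026 | 1.053 | 10.3–10.5% | 10.0% |
| 10 | 1.056 | 1.111 | 10.6–11.1% | 10.0% |
| 20 | 1.125 | 1.250 | 11.3–12.5% | 10.0% |
| 30 | 1.214 | 1.429 | 12.1–14.3% | 10.0% |

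If discontinued patients have no reactions (k = 0), the factor is 1.00.

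**Step 3. SOC/PT rows.** These have no administration-period limit. On reading A they can count a patient whom the overall row of the same table leaves out, so the parts need not agree with the total. On reading B they share the overall row's mismatch. On both readings an unrestricted numerator sits over an on-treatment denominator, and the Step 2 factors apply to these rows.

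**Step 4. Day 169–197 class.** The end date cannot pass Day 169, so at most 1 of the 29 days can count as on treatment.
- *Reading A:* only Day 169 can contribute. Reactions on Days 170–197 (28 days) are dropped from the class, including those in patients who are still on the drug but whose end date was capped.
- *Reading B:* all 29 days contribute, but the denominator is at best the patients still ongoing on Day 169. If nobody is regarded as receiving treatment after the end of treatment, it is zero and the percentage cannot be calculated. With an illustrative 3 patients having a reaction in the class, 3/100 followed is 3.0%. Against those ongoing on Day 169, 3/90 is 3.3%, 3/80 is 3.75% and 3/70 is 4.3%.

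**The case against.** The strongest reply is that the row directly below the denominator limits the numerator to the administration period, and that the SAP's only spelled-out use of the term is treatment start to end. On that reading the overall rows match through Day 168. This stands. A reader might infer from the shrinking denominator that percentages are inflated in every period. The documents do not establish that, because it requires reading B.

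A second reply is that leaving post-discontinuation reactions out of an on-treatment table is a choice of scope and the events are not lost. This also stands in part. Tables 2.1 and 2.3 keep these reactions over the full safety set. Tables 2.16.1 and 2.16.2 separate events during and after treatment, and Table 4.2 lists onset dates and causality. None of them, however, gives a reaction percentage by onset interval, and Tables 2.16.1 and 2.16.2 list adverse events rather than reactions.

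Third, the onset classes carry no test or decision rule: SAP section 9.13 covers change from baseline and background factors. In addition, a repeat of the same PT is counted once, at its earliest onset, which limits later counts. Both points reduce the consequence.

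None of these replies reaches the SOC/PT rows or the Day 169+ class. The SAP does have a category for patients ongoing at Day 169, so a count exists at that boundary. It would still be an on-treatment count over a class labelled as after treatment.

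**Conclusion.** The point holds as a mismatch in specification, not as proven inflation throughout. Two defects stand on either reading: the unrestricted SOC/PT rows over an on-treatment denominator, and a required last class in which at most 1 of 29 days can be on treatment. For the overall rows through Day 168 the factor is 1.00 on reading A. On reading B at equal risk it is 1.11, 1.25 or 1.43 with 10, 20 or 30 of 100 discontinued. Those counts are assumptions, so the actual size cannot be stated from the documents. The tables are descriptive and the events survive elsewhere, so no test result is affected. The correction should still be made, because the rules as written give incoherent percentages in the only planned tables of reaction frequency over time.

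**What to change.** In both tables, count all safety-period reactions, in the overall and SOC/PT rows alike, over patients under observation (on or off drug) at the start of each onset class. Define administration period or remove it from these rows.

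Give the Day 169+ class its own stated denominator, for example safety-set patients followed to Day 169. It needs one because protocol observation ends at 24 weeks while the class runs to start + 196 days.

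If an on-treatment version is also wanted, restrict numerator and denominator alike in every row, and use uncapped last-dose dates where available.

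Cost: SAP section 10 has no end-of-observation date, so one must be derived, with a rule for patients who stop attending. Two tables must be reprogrammed. No other analysis changes.
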